Appendix 2. Clinical Laboratory Tests

Safety Laboratory Tests

Hematology

Hematocrit Hemoglobin

Erythrocyte count (RBC) Mean cell volume Mean cell hemoglobin

Mean cell hemoglobin concentration

Leukocytes (WBC)

Platelets

Differential WBC absolute counts of:

Neutrophils Lymphocytes Monocytes Eosinophils

Basophils

Urinalysis

Specific gravity

рН

Protein

Glucose Ketones

Bilirubin Urobilinogen

Blood

Nitrite
Microscopy (if dipstick abnormal)

c 1

Serology

Hepatitis B surface antigen^a Hepatitis B core antibody^a Hepatitis C antibody^a

HIV^a

Clinical Chemistry

Sodium Potassium Bicarbonate Chloride Calcium

Glucose (random)

Blood urea nitrogen (BUN)

Uric acid

Total cholesterol
Total protein
Albumin
Total bilirubin
Direct bilirubin
Triglycerides

Alkaline phosphatase (ALP) Aspartate aminotransferase (AST) Alanine aminotransferase (ALT)

Creatinine

Phosphorus

Other tests

Pregnancy test (females only, if applicable)^b

FSH (females only, if applicable)^{a, c} QuantiFERON $^{\mathbb{R}}$ -TB Gold or TST a

Ethanol testing^d Urine drug screen^d

Abbreviations: FSH = follicle-stimulating hormone; HIV = human immunodeficiency virus; RBC = red blood cells; TST = tuberculin skin test; WBC = white blood cells.

- a Performed at screening only
- b Serum pregnancy test to be performed at screening. Urine pregnancy test to be performed at all other times.
- c FSH test performed for women \geq 50 and \leq 55 years of age who have had spontaneous amenhorrhea for \geq 6 months but \leq 1 year to confirm non-childbearing potential (\geq 40 mIU/mL).

d Urine drug screen and ethanol level will be performed locally at screening and at admission to the clinical research unit. Test may be repeated at additional time points at the discretion of the investigator.

Appendix 3. Study Governance, Regulatory and Ethical Considerations

Informed Consent

The investigator is responsible for:

- ensuring that the subject understands the nature of the study, the potential risks and benefits of participating in the study, and that their participation is voluntary.
- ensuring that informed consent is given by each subject or legal representative. This includes obtaining the appropriate signatures and dates on the informed consent form (ICF) prior to the performance of any protocol procedures and prior to the administration of investigational product.
- answering any questions the subject may have throughout the study and sharing in a timely manner any new information that may be relevant to the subject's willingness to continue his or her participation in the study.
- providing a copy of the ICF to the participant or the participant's legal representative and retaining a copy on file.

Recruitment

Lilly or its designee is responsible for the central recruitment strategy for subjects. Individual investigators may have additional local requirements or processes. Study specific recruitment material should be approved by Lilly.

Ethical Review

The investigator or appropriate local representative must give assurance that the ethical review board (ERB) was properly constituted and convened as required by International Council for Harmonisation (ICH) guidelines and other applicable laws and regulations.

Documentation of ERB approval of the protocol and the ICF must be provided to Lilly before the study may begin at the investigative site(s). Lilly or its representatives must approve the ICF before it is used at the investigative site(s). All ICFs must be compliant with the ICH guideline on good clinical practice.

The study site's ERB(s) should be provided with the following:

- the current IB and Summary of Product Characteristics and updates during the course of the study
- ICF
- relevant curricula vitae

Regulatory Considerations

This study will be conducted in accordance with the protocol and with:

- consensus ethics principles derived from international ethics guidelines, including the Declaration of Helsinki and Council for International Organizations of Medical Sciences International Ethical Guidelines
- 2) applicable ICH GCP Guidelines
- 3) applicable laws and regulations

Some of the obligations of the sponsor will be assigned to a third party organization.

Protocol Signatures

The sponsor's responsible medical officer will approve the protocol, confirming that, to the best of his or her knowledge, the protocol accurately describes the planned design and conduct of the study.

After reading the protocol, each principal investigator will sign the protocol signature page and send a copy of the signed page to a Lilly representative.

Final Report Signature

The lead investigator or designee will sign the clinical study report for this study, indicating agreement with the analyses, results, and conclusions of the report.

The sponsor's responsible medical officer and statistician will sign/approve the final clinical study report for this study, confirming that, to the best of his or her knowledge, the report accurately describes the conduct and results of the study.

Data Quality Assurance

To ensure accurate, complete, and reliable data, Lilly or its representatives will do the following:

- provide instructional material to the study sites, as appropriate.
- provide training to instruct the investigators and study coordinators. This training will give instruction on the protocol, the completion of the eCRFs, and study procedures.
- make periodic visits to the study site.
- be available for consultation and stay in contact with the study site personnel by mail, telephone, and/or fax.
- review and evaluate eCRF data and/or use standard computer edits to detect errors in data collection.
- conduct a quality review of the database.

In addition, Lilly or its representatives will periodically check a sample of the subject data recorded against source documents at the study site. The study may be audited by Lilly and/or regulatory agencies at any time. Investigators will be given notice before an audit occurs.

The investigator will keep records of all original source data. This might include laboratory tests, medical records, and clinical notes. If requested, the investigator will provide the sponsor, applicable regulatory agencies, and applicable ERBs with direct access to the original source documents.

Data Collection Tools/Source Data

An electronic data capture system will be used in this study. The site must define and retain all source records and must maintain a record of any data where source data are directly entered into the data capture system.

Data Protection

Data systems used for the study will have controls and requirements in accordance with local data protection law.

The purpose and use of subject personal information collected will be provided in a written document to the subject by the sponsor.

Study and Site Closure

Discontinuation of Study Sites

Study site participation may be discontinued if Lilly or its designee, the investigator, or the ERB of the study site judges it necessary for medical, safety, regulatory, or other reasons consistent with applicable laws, regulations, and GCP.

Discontinuation of the Study

The study will be discontinued if Lilly or its designee judges it necessary for medical, safety, regulatory, or other reasons consistent with applicable laws, regulations, and good clinical practice.

Appendix 4. Hepatic Monitoring Tests for Treatment-Emergent Abnormality

Selected tests may be obtained in the event of a treatment-emergent hepatic abnormality and may be required in follow-up with subjects in consultation with Lilly or its designee CRP.

Hepatic Hematology ^a	Haptoglobin ^a						
Hemoglobin							
Hematocrit	Hepatic Coagulation ^a						
RBC	Prothrombin Time						
WBC	Prothrombin Time, INR						
Neutrophils							
Lymphocytes	Hepatic Serologies ^{a,b}						
Monocytes	Hepatitis A antibody, total						
Eosinophils	Hepatitis A antibody, IgM						
Basophils	Hepatitis B surface antigen						
Platelets	Hepatitis B surface antibody						
	Hepatitis B Core antibody						
Hepatic Chemistrya	Hepatitis C antibody						
Total bilirubin	Hepatitis E antibody, IgG						
Conjugated bilirubin	Hepatitis E antibody, IgM						
Alkaline phosphatase							
ALT	Anti-nuclear antibodya						
AST	Alkaline Phosphatase Isoenzymesa						
GGT	Anti-smooth muscle antibody (or anti-actin						
CPK	antibody) ^a						

Abbreviations: ALT = alanine aminotransferase; AST = aspartate aminotransferase; CPK = creatinine phosphokinase; GGT = gamma-glutamyl transferase; Ig = immunoglobulin; INR = international normalized ratio; RBC = red blood cells; WBC = white blood cells.

- a Assayed by Lilly-designated or local laboratory.
- b Reflex/confirmation dependent on regulatory requirements and/or testing availability

Appendix 5. Blood Sampling Summary

This table summarizes the approximate number of venipunctures and blood volumes for all blood sampling (screening, safety laboratories, and bioanalytical assays) during the study.

Protocol I1F-MC-RHCS Sampling Summary

Purpose	Blood Volume per Sample (mL) ^b	Number of Blood Samples	Total Volume (mL) ^b	
Screening testsa	45 / 27.7	1	45 / 27.7	
Clinical laboratory testsa	12.5 / 11.7	6	75 / 70.2	
Pharmacokinetics	3	2	6	
Immunogenicity	10	3	30	
Pharmacogenetics	10	1	10	
Total			166 / 143.9	
Total for clinical purposes			170 / 150	

a Additional samples may be drawn if needed for safety purposes.

b Differing blood sample volumes pertain to different study sites.

Appendix 6. Protocol Amendment I1F-MC-RHCS (b)
Summary: A Randomized Study to Investigate
Injection-Site Pain Following Subcutaneous Injections of
2 Ixekizumab Test Formulations Compared to the
Commercial Formulation using a Pre-filled Syringe in
Healthy Subjects

Overview

Protocol I1F-MC-RHCS, A Randomized Study to Investigate Injection-Site Pain Following Subcutaneous Injections of 2 Ixekizumab Test Formulations Compared to the Commercial Formulation using a Pre-filled Syringe in Healthy Subjects, has been amended. The new protocol is indicated by Amendment (b) and will be used to conduct the study in place of any preceding version of the protocol.

Temperature assessments were added to each site visit. In addition, weekly safety telephone calls were added in between outpatient visits as appropriate.

The additional study activities were implemented to further monitor the health of subjects due to emerging data in response to a reporting of an SAE in the I1F-MC-RHCT study.

Enrollment into this study was paused in April 2019 to evaluate a potential safety concern observed in the I1F-MC-RHCT (PK Study). Approximately 80% of the VAS data had been collected; the team decided to conduct the protocol specified interim analysis based on all the available data, and stop enrolling new subjects.

Revised Protocol Sections

Note: All deletions have been identified by strikethroughs.

All additions have been identified by the use of underscore.

1. Protocol Synopsis

Subjects may be allowed to leave the CRU after completing the 4-hour safety assessments for Day 1, at the investigator's discretion. Subjects will be readmitted to the CRU on Days 7 and 14 to receive their second and third injections on Days 8 and 15, respectively, and may be allowed to leave the CRU after completing the 4-hour safety assessments at the investigators discretion on Days 8 and 15, respectively. Subjects will return to the CRU as an outpatient on Days 21 (± 1 day) and 43 (± 3 days) for a safety check-up. In addition, A safety follow-up telephone calls will be conducted in between outpatient visits, on Days 28 (± 1 day), 35 (± 3 days), 50 (± 3 days), ± 57 (± 3 days), and 64 (± 3 days), with a final safety follow-up telephone call on Day 71 (± 3 days). There will be a follow-up visit approximately 12 weeks after the last injection.

Safety and tolerability will be assessed by monitoring of adverse events (AEs), injection-site assessments, injection-site pain, bleeding/bruising assessments, Columbia Suicide Severity Rating Scale (C-SSRS), Hospital Anxiety Depression Scale (HADS), vital signs assessments, temperature, physical examination, 12-lead electrocardiograms (ECGs), and clinical laboratory tests. Pain assessments will be made using an injection-site visual analog scale (VAS).

2. Schedule of Activities

	Screening	Study Day												
Procedure	-28 to -2 days prior to Day 1	Day -1	Day 1	Day 7	Day 8	Day 14	Day 15	Day 21 (± 1 day)	Days 28 & 35 (± 3 days)	Day 43 (± 3 days)	Days 50, 57, & 64 (± 3 days)	Day 71 (± 3 days)	Follow-up FU/ EDa -12 weeks post injection (±1 week)	Comments
Safety Assessment (Telephone Call)									X		X	X	(±1 week)	Every effort will be made to contact subjects as near to this time as possible but missed calls will not be recorded as protocol deviations. Subjects will be asked about the occurrence of AEs; injection-site reactions, and concomitant medication use.
Body Temperature			P	X		X		X		X			X	

Adverse Events and Concomitant	X	X	X	X	X	X	X	X	X	X	X	X	X	
Medication														

^a Follow-up / Early Discontinuation should be ~12 weeks post last injection (±1 week).

5. Study Design

5.1 Overall Design

Subjects may be allowed to leave the CRU after completing the 4-hour safety assessments for Day 1, at the investigator's discretion. Subjects will be readmitted to the CRU on Days 7 and 14 to receive their second and third injections on Days 8 and 15, respectively, and may be allowed to leave the CRU after completing the 4-hour safety assessments at the investigators discretion on Days 8 and 15, respectively. Subjects will return to the CRU as an outpatient on Days 21 (± 1 day) and 43 (± 3 days) for a safety check-up. In addition, A safety follow-up telephone calls will be conducted in between outpatient visits, on Days 28 (± 1 day), 35 (± 3 days), 50 (± 3 days), ± 3 days), and 64 (± 3 days), with a final safety follow-up telephone call on Day 71 (± 3 days). There will be a follow-up visit approximately 12 weeks after the last injection.

Safety and tolerability will be assessed by monitoring of AEs, injection-site assessments, injection-site pain, bleeding/bruising assessments, Columbia Suicide Severity Rating Scale (C-SSRS), Hospital Anxiety and Depression Scale (HADS), vital signs assessments, temperature, physical examination, 12-lead electrocardiograms (ECGs), and clinical laboratory tests.

5.4 Scientific Rationale for Study Design

All doses will be administered by clinical site staff to reflect safety and tolerability of the device during its intended usage.

7.1.2. Medical Device

The investigator or his/her designee will ensure that the instructions have been followed properly; maintaining accurate records of study devices, dispensing, and collection. The used or unused PFS may be destroyed by a qualified vendor. However, a used PFS with a product complaint will need to be returned to Lilly.

9.2. Adverse Events

The investigator will interpret and document whether or not an AE has a reasonable possibility of being related to study treatment, study device, or a study procedure, taking into account concomitant treatment or pathologies.

A "reasonable possibility" means that there is a potential cause and effect relationship between the IP, study device and/or study procedure and the AE.

9.3. Treatment of Overdose

For the purposes of this study, an overdose of ixekizumab is considered any dose higher than the dose assigned through randomization. Syringes Devices used in this study can deliver only 1 mL volume of ixekizumab.

9.4. **Safety**

Safety will be assessed throughout the course of the study at site visits and via telephone calls in between site visits.

9.4.4. Temperature

Body temperature will be assessed at the times indicated in the Schedule of Activities (Section 2).

10.2.3. Treatment Compliance

Every attempt will be made to select subjects who have the ability to understand and comply with instructions. Noncompliant subjects may be discontinued from the study. The time and day of administration of ixekizumab injections will be recorded. Device accountability records will be maintained by the study site.

The specifications in this protocol for the timings of safety assessments are given as targets, to be achieved within reasonable limits. Modifications may be made to the time points based upon the safety information obtained. The scheduled time points may be subject to minor alterations; however, the actual time must be correctly recorded in the eCRF.

10.3.2. Data Review During the Study

Data will be reviewed by the investigator and Sponsor throughout the course of the study to ensure subject safety.

10.3.3. Interim Analyses

One formal interim analysis is planned for this study. The interim analysis will include review of all available subjects' safety data (AEs, VAS, and ISR data) collected up to and including Day 21.

#### 2. ABBREVIATIONS

Abbreviations pertain to the Statistical Analysis Plan (SAP) only (not the tables, figures and listings [TFLs]).

AE Adverse event

ALP Alkaline phosphatase

ALT Alanine aminotransferase

CRF Case Report Form

CRU Clinical Research Unit
CSR Clinical Study Report

C-SSRS Columbia Suicide Severity Rating Scale

EC Early Clinical

ECG Electrocardiogram

e.g. For example (Latin: *exempli gratia*)

ICH International Conference on Harmonisation

ISR Injection site reaction

HADS Hospital Anxiety and Depression Scale

MedDRA Medical Dictionary for Regulatory Activities

MRE Magnetic resonance elastography

SAP Statistical Analysis Plan

SC Subcutaneous

SD Standard deviation

TBL Total bilirubin

TFLs Tables, Figures, and Listings

ULN Upper limit of normal VAS Visual Analog Scale

WHO World Health Organization

Final, 8 January 2019 Page 3 of 10

#### 3. INTRODUCTION

This SAP has been developed after review of the Clinical Study Protocol (final version dated 29 October 2018 and amendment (a) dated 03 December 2018).

This SAP describes the planned analysis of the safety and tolerability data from this study. A detailed description of the planned TFLs to be presented in the clinical study report (CSR) is provided in the accompanying TFL shell document.

The intent of this document is to provide guidance for the statistical analyses of data. In general, the analyses are based on information from the protocol, unless they have been modified by agreement between Eli Lilly and Company and Covance Early Clinical (EC) Biometrics. A limited amount of information concerning this study (e.g., objectives, study design) is given to help the reader's interpretation. This SAP must be signed off prior to first subject administration for this study. When the SAP and TFL shells are agreed upon and finalized, they will serve as the template for this study's CSR.

This SAP supersedes the statistical considerations identified in the protocol; where considerations are substantially different, they will be so identified. If additional analyses are required to supplement the planned analyses described in this SAP, they may be performed and will be identified in the CSR. Any substantial deviations from this SAP will be agreed upon between Eli Lilly and Company and Covance EC Biometrics and identified in the CSR. Any minor deviations from the TFLs may not be documented in the CSR.

This SAP is written with consideration of the recommendations outlined in the International Conference on Harmonisation (ICH) E9 Guideline entitled Guidance for Industry: Statistical Principles for Clinical Trials and the ICH E3 Guideline entitled Guidance for Industry: Structure and Content of Clinical Study Reports.

#### 4. STUDY OBJECTIVES

#### 4.1 Primary Objective

Evaluate pain intensity on injection of ixekizumab with different formulations.

#### 4.2 Exploratory Objective

To evaluate the safety and tolerability of a single 80 mg subcutaneous (SC) dose of ixekizumab Test Formulation 1 and Test Formulation 2 compared to the commercial formulation (Reference).

#### 5. STUDY DESIGN

This will be a single-dose, subject-blind, 3-period, 3-formulation, randomized, crossover study in healthy subjects.

All subjects will be screened within 28 days prior to enrollment. Eligible subjects will be admitted to the clinical research unit (CRU) on Day -1 and randomized 1:1:1 to 1 of 3 possible

[figure not shown]
Final, 8 January 2019 Page 4 of 10

formulation sequences (see Figure 1). On Day 1, subjects will receive a single 1-mL SC injection of 1 of the following formulations, according to the randomization schedule:

- 80 mg ixekizumab Commercial Formulation (Reference)
- 80 mg ixekizumab Test Formulation 1
- 80 mg ixekizumab Test Formulation 2

Subjects may be allowed to leave the CRU after completing the 4-hour safety assessments for Day 1, at the investigator's discretion. Subjects will be readmitted to the CRU on Days 7 and 14 to receive their second and third injections on Days 8 and 15, respectively, and may be allowed to leave the CRU after completing the 4-hour safety assessments at the investigator's discretion on Days 8 and 15, respectively. Subjects will return to the CRU as an outpatient on Days 21 ( $\pm$  1 day) and 43 ( $\pm$  3 days) for a safety check-up. A safety follow-up telephone call will be conducted on Day 71 ( $\pm$  3 days). There will be a follow-up visit approximately 12 weeks after the last injection.

#### Group 1

Subjects will be blinded to all treatments.

Figure 1. Illustration of study design.

Final, 8 January 2019 Page 5 of 10

#### 6. FORMULATIONS

The following is a list of the study formulation abbreviations that will be used in the TFLs.

Study Formaulation Name	Abbreviation	Formulation order in TFL
80 mg ixekizumab Commercial Formulation	Reference	1
80 mg ixekizumab Test Formulation 1	Test Formulation 1	2
80 mg ixekizumab Test Formulation 2	Test Formulation 2	3

#### 7. SAMPLE SIZE JUSTIFICATION

Up to 102 subjects may be enrolled to maximize the intent to have 78 subjects (26 subjects per formulation sequence) complete the study.

The objective of this study is to evaluate the injection pain immediately following dosing.

Because of the crossover study design, each subject will have the opportunity to receive each formulation.

#### 8. DEFINITION OF ANALYSIS POPULATION

The "Safety" population will consist of all subjects who received at least one dose of study drug, whether or not they completed all protocol requirements.

All protocol deviations that occur during the study will be considered for their severity/impact and will be taken into consideration when subjects are assigned to this analysis population.

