8.1.1. Discontinuation of Inadvertently Enrolled Subjects

If the sponsor or investigator identifies a subject who did not meet enrollment criteria and was inadvertently enrolled, a discussion must occur between the Lilly CP/CRP and the investigator to determine if the subject may continue in the study. If both agree it is medically appropriate to continue, the investigator must obtain documented approval from the Lilly CP/CRP to allow the inadvertently enrolled subject to continue in the study with or without continued treatment with IP.

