9.4.5.2. Bleeding/Bruising Assessment

All injection sites will be observed at the times indicated in the Schedule of Activities (Section 2) by the blinded assessor, and the presence of visible bleeding/bruising will be recorded on the eCRF. A bandage may be placed on the injection site after assessment.

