10.3. Statistical Analyses

Statistical analysis of this study will be the responsibility of Eli Lilly and Company or its designee.

Safety analyses will be conducted for all enrolled subjects who receive at least 1 dose of study drug, whether or not they completed all protocol requirements.

Continuous data will be summarized in terms of the mean, standard deviation, minimum, maximum, median, and number of observations. Categorical data will be summarized as frequency counts and percentages.

Any change to the data analysis methods described in the protocol, and the justification for making the change, will be described in the clinical study report. Additional exploratory analyses of the data will be conducted as deemed appropriate. Complete details of the planned analyses will be documented in the Statistical Analysis Plan.

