10.3.1.2.2. Statistical Evaluation of Other Safety Parameters

Abnormal lab values will be listed. Other safety parameters that will be assessed include injection-site assessments, including pain, induration, swelling, pruritus, bleeding/bruising, and erythema/redness. The parameters will be listed and summarized using standard descriptive statistics. Suicidal ideation and/or behavior and self-injurious behavior with no suicidal intent, based on the C-SSRS, will be listed by subject. Only subjects that show suicidal ideation/behavior or self-injurious behavior without suicidal intent will be included in the listing (ie, if a subject answers are all 'no' for the C-SSRS, then that subject will not be displayed). HADS item scores will be listed for subjects with HADS depression sub-scale ≥11 at any time. Additional analyses may be performed if warranted upon review of the data.

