#### 9. STATISTICAL METHODOLOGY

#### 9.1 General

Data listings will be provided for all data that are databased. Summary statistics and statistical analysis will only be presented for data where detailed in this SAP. For continuous data, summary statistics will include the arithmetic mean, arithmetic SD, median, min, max and N. For categorical data, frequency count and percentages will be presented. Data listings will be provided for all subjects up to the point of withdrawal, with any subjects excluded from the relevant population highlighted. Summary statistics and statistical analyses will generally only be performed for subjects included in the relevant analysis population. For the calculation of summary statistics and statistical analysis, unrounded data will be used.

Final, 8 January 2019 Page 6 of 10

Mean change from baseline is the mean of all individual subjects' change from baseline values. Each individual change from baseline will be calculated by subtracting the individual subject's baseline value from the value at the timepoint. The individual subject's change from baseline values will be used to calculate the mean change from baseline using a SAS procedure such as Proc Univariate.

Data analysis will be performed using SAS® Version 9.4 or greater.

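### SAP 8 puts every dosed subject in its only analysis population, then lets protocol deviations bear on membership; two safety summaries planned in the protocol are also missing, so SAP 12's declaration of no changes is inaccurate

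*SAP*

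**What the plan says.** **Population.** SAP section 8 defines one population, Safety: "all subjects who received at least one dose of study drug, whether or not they completed all protocol requirements". It then says that all protocol deviations "will be considered for their severity/impact and will be taken into consideration when subjects are assigned to this analysis population". Protocol section 10.3 has the same all-dosed rule, "Safety analyses will be conducted for all enrolled subjects who receive at least 1 dose of study drug, whether or not they completed" (the sentence goes on to cover all protocol requirements), and no clause about deviations. SAP section 9.1 adds "Summary statistics and statistical analyses will generally only be performed for subjects included in the relevant analysis population", and says that listings will highlight any subject excluded from the relevant population.

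**Injection-site items.** Protocol section 10.3.1.2.2 names pain, induration, swelling, pruritus, "bleeding/bruising, and erythema/redness. The parameters will be listed and summarized using standard descriptive statistics". Protocol section 9.4.5.2 confirms that "the presence of visible bleeding/bruising will be recorded on the eCRF". SAP section 9.3.9 provides a frequency table by formulation for induration, swelling, pruritus and erythema/redness only.

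**Adverse events.** Protocol section 10.3.1.1 plans incidence per treatment by severity and by the investigator's view of association with study drug. SAP section 9.3.1 plans tables by formulation and severity, and by formulation, system organ class and preferred term, all irrespective of causality.

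**Closure and declaration.** SAP section 9.1 states "Summary statistics and statistical analysis will only be presented for data where detailed in this SAP". SAP section 12 declares that nothing differs from the protocol-specified analyses.

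**The concern.** If one dose is enough for membership, a deviation has nothing to decide unless it can remove a dosed subject, and the definition rules that out. The two sentences therefore do not give one answer for a dosed subject with an important deviation. The plan states no criteria, no decision-maker and no date for the judgement.

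The only population defined is the one affected, so the primary VAS comparison inherits the problem. The interim analysis sharpens it. Protocol Appendix 1 defines an interim analysis as one on data separated into treatment groups, and protocol section 10.3.3 includes VAS in it. With no date fixed, a decision on membership could follow sight of VAS results by formulation.

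The missing summaries are a lesser matter. At stake is whether the report presents the safety tables the protocol planned, and whether a reader can rely on SAP section 12 as a record of departures.

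**Working it through.** The documents give no figure for this point to reproduce, so the main check sets the texts side by side.

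**1. Does the primary analysis inherit the ambiguity?** SAP section 8 defines no other population. SAP section 9.1 generally restricts statistics to the relevant population. The VAS model in SAP section 9.3.10 names none of its own. The protocol places the same model under Safety Analyses (10.3.1.2.1), where the all-dosed rule of 10.3 applies. So it does.

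**2. A foreseeable case.** Protocol section 8.1.1 allows documented approval "to allow the inadvertently enrolled subject to continue in the study with or without continued treatment with IP". Take such a subject who is dosed three times.
- Under the first sentence of SAP section 8, the subject is in.
- Under the second, the breach of eligibility is weighed and the outcome is open.
- Under protocol section 10.3, the subject is in.

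**3. How much primary data one exclusion removes.** A fully dosed subject gives 3 zero-minute VAS values, one per period.
- 78 completers (protocol section 5.2): 78 × 3 = 234; 3/234 = 1.3%.
- All 102 enrolled and dosed three times: 102 × 3 = 306; 3/306 = 1.0%.
- About 80% of VAS data collected (protocol Appendix 6), assuming this refers to the 234: 0.8 × 234 ≈ 187; 3/187 = 1.6%.

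These are shares of data, not estimates of bias. Without an SD, margin or deviation rate in the documents, the shift in a treatment difference cannot be calculated.

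**4. Injection-site items other than pain.**

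| Item | Protocol 10.3.1.2.2 | SAP 9.3.9 |
|---|---|---|
| Induration | yes | yes |
| Swelling | yes | yes |
| Pruritus | yes | yes |
| Erythema/redness | yes | yes |
| Bleeding/bruising | yes | no |

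The protocol has 5 items and the SAP 4. Bleeding/bruising appears nowhere in the SAP, so under the closure rule in SAP section 9.1 only a listing remains. From the Schedule of Activities, each subject has 7 time points × 3 periods + Day 21 + Day 43 = 23 scheduled assessments. For 78 subjects that is 23 × 78 = 1,794, listed but not summarized.

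**5. Adverse events by association.** The protocol plans this breakdown and SAP section 9.3.1 names none. The table shells were not available to check.

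**6. Could version timing explain the differences?** The SAP (final, 8 January 2019) was written against the protocol up to amendment (a). The revisions that amendment (b) lists in Appendix 6 do not include the population text of 10.3, nor 10.3.1.1 or 10.3.1.2.2. The protocol text therefore evidently predates the SAP.

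**The case against.** The strongest reply is that SAP section 8 contains no exclusion rule. The definition is the operative sentence, and the next says only that deviations will be weighed. A dosing deviation such as an incomplete injection could bear on whether a subject received a dose at all, and on that reading the sentences agree. It is right that the SAP does not say any dosed subject will be excluded. But the clause covers every deviation and weighs its severity or impact, which is far wider than establishing whether a dose was given, and SAP section 9.1 provides for excluded subjects. The reading is strained, and the text does not settle the matter.

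It can also be said that protocol section 8.1.1 concerns medical agreement to continue, not analysis membership. That is so; it serves here only to show that dosed subjects with an eligibility breach are foreseen.

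On the omissions, several points stand. They are descriptive, listings remain, and the injection-site and bleeding/bruising assessors are blinded (protocol section 7.3). A bleeding or bruising event reported as an adverse event would still be tabulated. The adverse-event point is the weaker of the two: protocol section 10.3.1.1 opens by making safety summaries depend on event frequency, an all-causality table does not expressly bar a further breakdown, and the shells might contain one. Against that, SAP section 9.1 ties statistics to what the SAP itself details.

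SAP section 3 promises to identify only substantial differences, so the sponsor may regard these as minor. That may excuse not flagging them; it does not make an unqualified statement of no changes accurate.

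Finally, the 102-subject figure is only an outer bound, since Appendix 6 records a decision to stop enrolling.

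**Conclusion.** The concern holds. SAP section 8 leaves open whether a dosed subject with an important deviation enters the primary VAS analysis, and it departs from protocol section 10.3 without saying so. The documents do not show that anyone was or will be excluded. Each exclusion of a fully dosed subject would cost 1.0% to 1.6% of the zero-minute values, depending on the denominators assumed above; the effect on the VAS difference is unknown. The larger weakness is that the judgement has no criteria and could be made after the interim.

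The bleeding/bruising omission is established from the SAP text. The adverse-event omission is established for the SAP text but not for the unseen shells. Both are minor in consequence, and together they make SAP section 12 inaccurate. This should be corrected, chiefly because of the population sentence.

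**What to change.** - **SAP section 8:** delete the deviation sentence, so that all dosed subjects with VAS data enter the primary analysis. Confine any deviation-based exclusion to a labelled sensitivity analysis whose criteria are written down without reference to results by formulation. For data already in the interim analysis, state that the criteria were set afterwards if that is the case.
- **SAP section 9.3.9:** add bleeding/bruising to the frequency table by formulation.
- **SAP section 9.3.1:** add a table of treatment-emergent events by relationship to study drug, or declare its omission.
- **SAP section 12:** list whatever differences from the protocol remain.

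The cost is one sentence deleted, one section reworded and one or two descriptive tables from data already collected, plus the re-versioning of a SAP marked final. No new data are needed. The sensitivity analysis is needed only if the sponsor wants deviation-based exclusions.
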